## 8. STUDY OBJECTIVES

### 8.1 Primary Objectives

The primary objective is to determine, for the patients with baseline CIS:

- The proportion that achieves a complete response (CR) after treatment with inodiftagene vixteplasmid

### 8.2 Secondary Objectives

The secondary objectives are to determine the:

- Proportion of patients with absence of high-grade recurrent or persistent disease at 48 weeks (overall population and subgroup of patients with CIS)
- Proportion of patients with absence of high-grade recurrent or persistent disease at 12, 24, 36, 72, and 96 weeks (overall population and subgroup of patients with CIS)
- Time to recurrence (Kaplan-Meier plot)
- Proportion of patients who are progression-free at 48, 72, and 96 weeks
- Overall survival of patients enrolled in the study at 48, 72, and 96 weeks
- Quality of life in patients treated with inodiftagene vixteplasmid
- Assessment of safety

## 9. INVESTIGATIONAL PLAN

### 9.1 Overall Study Design and Plan—Description

This study, BC-819-18-204 (referred to as Study 204), is a Phase 2, open-label, monotherapy, single-arm, multicenter clinical trial of BC-819 (inodiftagene vixteplasmid) in patients with NMIBC adequately treated with BCG whose disease is BCG-unresponsive according to the FDA guidance ([FDA 2018](#)). Patients with BCG-unresponsive disease have NMIBC that is unlikely to benefit from and should not be treated with further intravesical BCG.

Patients are to have recurred or progressed after adequate treatment, had BCG-unresponsive disease, had a TUR, and then had all papillary disease completely resected and obvious CIS disease fulgurated when indicated. Patients with T1 disease should undergo resection of the base of the lesion when possible (biopsy should contain muscle fiber). Patients must have 1 or more of the following: completely resected high-grade T1 disease, CIS disease, or completely resected high-grade Ta disease. There is no intravesical or medical standard of care for this patient population, and the usual course is radical cystectomy.

A total of 140 patients who meet study entry criteria will be enrolled and treated during the approximately 15-month enrollment period. The first 35 patients enrolled and treated must have CIS (with or without papillary disease). After these 35 patients are treated and 10 complete responders are documented, the enrollment will expand to also allow patients with papillary disease only who meet inclusion and exclusion criteria. It is estimate that a total of approximately 70 to 100 patients with CIS will be treated.

All enrolled patients will enter the 10-week induction phase and begin treatment with BC-819. Treatment should begin within 7 days of enrollment and  $\leq$ 42 days from the last TUR or biopsy. During the induction phase, patients will receive an intravesical instillation of BC-819 at a dose of 20 mg/50 mL aqueous solution once per week for 10 weeks according to the induction phase treatment schedule (see [Table 12.1](#)).

Upon completion of the induction phase, patients will continue with maintenance therapy of BC-819 every 3 weeks beginning at Week 12 (Visit 11) and continuing for the next 84 additional weeks until the end of the study, defined as completion of the 96-week visit (Visit 39).

During the study, patients will undergo repeat direct visualization (ie, cystoscopy  $\pm$  biopsy and cytology) and re-TUR (as needed for cause) every 12 weeks during the first and second year. Patients with persistent CIS which does not resolve by the 12-week assessment, or at subsequent 12-week assessments, or who have recurrence or new evidence of CIS or high-grade papillary disease at any time will be discontinued and classified as nonresponders and recurrences in the primary and secondary endpoint analyses. Patients benefiting from treatment, with no documented high-grade recurrence or progression, will continue to receive maintenance therapy every three weeks. Appearance or persistence of lower grade tumors will not be considered as recurrence for the primary and secondary endpoint analyses, and patients with only low-grade tumors should continue treatment after resection and histological confirmation.

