## 11. EFFICACY AND SAFETY ASSESSMENTS

### 11.1 Primary Efficacy Variable

The primary efficacy endpoint is, in patients with CIS at baseline, the:

- Proportion that achieves a CR at any time on or after week 12 and within the first 48 weeks

Complete response is defined as at least one of the following:

- Negative cystoscopy and negative (including atypical) urine cytology
- Positive cystoscopy with biopsy-proven benign or low-grade NMIBC and negative cytology
- Negative cystoscopy with malignant urine cytology if cancer is found in the upper tract or prostatic urethra and random bladder biopsies are negative

The complete response in patients with CIS for this endpoint must be documented on or after the Week 12 response assessment and on or prior to the Week 48 assessment. Duration of complete response in patients with CIS will be calculated from the documented onset of the complete response to the assessment where the patient no longer meets the definition of complete response. More generally, recurrence is defined as the reappearance or persistence of high-grade disease, or new high-grade disease. Recurrence must be biopsy proven. Persistence, appearance, or presence of lower grade disease will not be considered recurrence.

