### **13.5 Efficacy Analysis**

#### **13.5.1 Primary Efficacy Analysis**

The primary endpoint of the study is the CR rate in patients with CIS, supported by duration of the complete response.

A CR in patients with CIS is defined as at least one of the following:

- Negative cystoscopy and negative (including atypical) urine cytology
- Positive cystoscopy with biopsy-proven benign or low-grade NMIBC and negative cytology
- Negative cystoscopy with malignant urine cytology if cancer is found in the upper tract or prostatic urethra and random bladder biopsies are negative

The complete response in patients with CIS for this endpoint must be documented on or after the Week 12 response assessment and on or prior to the Week 48 assessment. The durability of the CRs will be described using Kaplan-Meier Plots of the duration of CR in responders. Duration of complete response in patients with CIS will be calculated from the documented onset of the complete response to the assessment where the patient no longer meets the definition of complete response. More generally, Recurrence is defined as the reappearance or persistence of high-grade disease or new high-grade disease. Recurrence must be biopsy proven. Persistence, appearance, or presence of lower grade disease will not be considered recurrence. Sensitivity analyses for duration of response will be performed starting from the time the CIS lesion clears to time that new CIS lesions are identified, censoring patients with no CIS but other high-grade disease at the time of recurrence and a separate analysis looking at the time from response until any NMIBC is found (including low-grade disease).

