The population for this study is patients with high-risk NMIBC whose disease is unresponsive to BCG. This is a patient population for which treatment options are limited and outcomes are usually poor. In this setting, a single-arm Phase 2 clinical study with complete response rate as the primary endpoint can provide primary evidence of effectiveness to support a marketing application.

The primary endpoint of this study will be to determine in patients with baseline CIS, the proportion of patients that experience a complete response (CR). In this study, in accordance with the US Food and Drug Administration (FDA) guidance, complete response is defined as negative urine cytology and no lesions visible on cystoscopy, negative urine cytology with biopsy proven benign or low-grade NMIBC, or negative cystoscopy with malignant urine cytology, if cancer is found in the upper tract or prostatic urethra and random bladder biopsies are negative. Additionally, the duration of the response will be determined. Recurrence is defined as the reappearance or persistence of high-grade disease. Recurrence must be biopsy proven. Persistence, appearance, or presence of lower grade disease will not be considered.

This document is confidential.

recurrence. Additionally, patients with appearance of new high-grade disease (ie, new high-grade papillary disease in patients with CIS only or new CIS in patients with papillary disease only) will be classified as failures, as will patients with CIS at baseline whose CIS lesions have not resolved by the 12-week cystoscopy or who have CIS or high-grade papillary disease at later timepoints.

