During the study, patients will undergo repeat direct visualization (ie, cystoscopy ± biopsy and cytology) and re-TUR (as needed for cause) every 12 weeks during the first and second year. Patients with persistent CIS which does not resolve by the 12-week assessment, or at subsequent 12-week assessments, or who have recurrence or new evidence of CIS or high-grade papillary disease at any time will be discontinued and classified as nonresponders and recurrences in the primary and secondary endpoint analyses. Patients benefiting from treatment, with no documented high-grade recurrence or progression, will continue to receive maintenance therapy every three weeks. Appearance or persistence of lower grade tumors will not be considered as recurrence for the primary and secondary endpoint analyses, and patients with only low-grade tumors should continue treatment after resection and histological confirmation.

This document is confidential.

4. Schedule of Assessments

The administration of BC-819 is separated into 2 phases, the induction phase and the maintenance phase.

During the induction phase, eligible patients will receive BC-819 once per week for 10 consecutive weeks.

The flow chart for the induction phase is

This document is confidential.

Table 1.

During the maintenance phase, patients will transition to once every 3 weeks administration of BC-819 and will be evaluated every 12 weeks by cystoscopy for staging of response in order to determine continued participation. The urine cytology and cystoscopy must be completed within 14 days prior to the next administration of BC-819 and fully evaluated before initiating the treatment. The flow charts for the maintenance phase are Table 2 and Table 3.

This document is confidential.

Table 1 Induction Phase

Visit	Screening	V1	V2	V3	V4	V5	V6	V7	V8	V9	V10
Day	≤42 days before V1	1	8	15	22	29	36	43	50	57	64
Baseline only procedures	X										
Interim physical examination including ECOG performance status	X	X	X	X	X	X	X	X	X	X	X
Vital signs	X	X	X	X	X	X	X	X	X	X	X
Complete blood count and biochemical profile	X										
Urine sample for urinalysis (routine and microscopic)	X										
Urine sample for culture and sensitivity	X										
Urine sample for cytology	X										
Adverse events	X	X	X	X	X	X	X	X	X	X	X
Prior and concomitant medications	X	X	X	X	X	X	X	X	X	X	X
Biopsy	X										
Cystoscopy	X										
TUR/re-TUR	X										
QOL assessment		X									
Administration of BC-819		X	X	X	X	X	X	X	X	X	X

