5.1 Efficacy Endpoints

5.1.1 Primary Efficacy Endpoint

The primary efficacy endpoint is, in patients with CIS at baseline, the:

- Proportion that achieves a CR at any time on or after week 12

Complete response is defined as at least one of the following:

- Negative cystoscopy and negative (including atypical) urine cytology
- Positive cystoscopy with biopsy-proven benign or low-grade NMIBC and negative cytology
- Negative cystoscopy with malignant urine cytology if cancer is found in the upper tract or prostatic urethra and random bladder biopsies are negative

The complete response in patients with CIS for this endpoint must be documented on or after the Week 12 response assessment. Duration of complete response in patients with CIS will be calculated from the documented onset of the complete response to the assessment where the patient no longer meets the definition of complete response. More generally, recurrence is defined as the reappearance or persistence of high-grade disease, or new high-grade disease. Recurrence must be biopsy proven. Persistence, appearance, or presence of lower grade disease will not be considered recurrence.

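### The design overview calls every later relapse a nonresponse in the primary analysis, contradicting the endpoint sections, where one documented CR counts and later loss only ends its duration

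*Protocol*

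**What the plan says.** **Overview sentence.** Protocol 9.1 states that patients "who have recurrence or new evidence of CIS or high-grade papillary disease at any time will be discontinued and classified as nonresponders and recurrences", and applies this to the primary and secondary endpoint analyses alike. The Synopsis (Study Design) has the same sentence. SAP 3.1 repeats it: such patients "will be discontinued and classified as nonresponders and recurrences in the primary and secondary endpoint analyses".

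**Rationale text.** Protocol 7.5 and SAP 1, in the paragraph that introduces the primary endpoint, list as failures patients with uncleared CIS at Week 12 "or who have CIS or high-grade papillary disease at later timepoints". Neither names the analysis concerned.

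**Endpoint and analysis sections.** Protocol 11.1 defines the primary endpoint as "Proportion that achieves a CR at any time on or after week 12 and within the first 48 weeks". Protocol 13.5.1 requires only that the CR "must be documented on or after the Week 12 response assessment and on or prior to the Week 48 assessment". SAP 5.1.1 has "Proportion that achieves a CR at any time on or after week 12", and SAP 7.3.1 follows it. None of these sections asks that the CR be kept. Loss of CR enters through duration: "The durability of the CRs will be described using Kaplan-Meier Plots of the duration of CR in responders".

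**The concern.** Take a patient with baseline CIS, a CR at Week 12 and biopsy-proven high-grade disease at Week 24. Protocol 11.1 and 13.5.1 make this patient a responder whose duration of CR has ended. Protocol 9.1 makes the same patient a nonresponder in the primary analysis. The overview sentence has no time limit, so a relapse at Week 72 would have the same effect.

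This affects the numerator of the primary endpoint in an open-label, single-arm study that Protocol 7.5 presents as possible primary evidence for a marketing application. If the rule is settled only after relapses have been seen, the primary result depends on that choice. The overview rule also clashes with the planned duration analysis: if relapsers were nonresponders, the duration curve in responders would contain no high-grade relapse events.

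**Working it through.** **1. Which rule does the rest of the text support?**

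| Place | What it does with relapse after a CR |
|---|---|
| Synopsis, Protocol 9.1, SAP 3.1 | Nonresponder and recurrence, primary and secondary analyses |
| Protocol 7.5, SAP 1 | Failure, analysis not named |
| Protocol 11.1, 13.5.1; SAP 5.1.1, 7.3.1 | CR counts; loss ends its duration |
| Synopsis (discontinuation), Protocol 9.6 | Primary-analysis nonresponder label given only to CIS that fails to clear; recurrence after clearance is a separate item without it |
| Protocol 11.2, SAP 5.1.2 | New high-grade disease and recurrent CIS are failures in the EFS analyses |
| Protocol 13.5.2, SAP 7.5 | Interim count is of patients who achieve a CR; no earlier CR is removed |

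Only the overview sentence explicitly removes a relapser from the primary numerator.

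**2. Reproducing the plan's figures.** Inputs from Protocol 13.1: null rate 20%, two-sided 0.05, exact binomial. The critical value r is the smallest count with P(X ≥ r | n, 0.20) ≤ 0.025, which is when the Clopper-Pearson lower limit exceeds 20%.

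- n = 70: r = 22 (tail 0.0159; 21 gives 0.0303). P(X ≥ 22 | 70, 0.40) = 94.5%. The plan says over 95%, so this is marginally below its wording.
- n = 100: r = 29 (tail 0.0200; 28 gives 0.0342). P(X ≥ 29 | 100, 0.35) = 91.5%. The plan says about 92%.
- Interim (Protocol 13.5.2): P(X ≥ 10 | 35, 0.40) = 94.2% and P(X ≤ 9 | 35, 0.15) = 97.1%. Both match the plan.

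These figures treat the endpoint as ever-CR.

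**3. Effect of the overview sentence if followed literally.** Suppose 28 of 70 patients have a documented CR and k of them have an observed relapse. The count becomes 28 − k, with limits Beta⁻¹(0.025; x, n − x + 1) and Beta⁻¹(0.975; x + 1, n − x).

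| k | Share of the 28 CRs | CRs/70 | 95% CI | Excludes 20%? |
|---|---|---|---|---|
| 0 | 0% | 28 (40.0%) | 28.5–52.4% | Yes |
| 6 | 21.4% | 22 (31.4%) | 20.9–43.6% | Yes |
| 7 | 25.0% | 21 (30.0%) | 19.6–42.1% | No |
| 8 | 28.6% | 20 (28.6%) | 18.4–40.6% | No |
| 14 | 50.0% | 14 (20.0%) | 11.4–31.3% | No |

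**4. Chance of excluding 20%.** The documents give no relapse share f, so the range is assumed. If each responder relapses independently with probability f, the counted rate is p(1 − f). Single-stage results, ignoring the futility look:

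| f | n = 70, true CR 40% | n = 100, true CR 35% |
|---|---|---|
| 0% | 94.5% | 91.5% |
| 10% | 82.1% | 73.8% |
| 20% | 58.5% | 44.9% |
| 30% | 30.2% | 17.5% |
| 50% | 1.6% | 0.3% |

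For example, at f = 20% and n = 70 the counted rate is 0.40 × 0.80 = 0.32, and P(X ≥ 22 | 70, 0.32) = 58.5%.

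**The case against.** The strongest reply is that the sentence is loose drafting and was never the analysis rule. It covers all patients, including those with papillary disease only, who are not in the primary analysis. It pools two groups, two labels and two analyses. Read group by group, persistent CIS is a primary nonresponse and relapse is a secondary-endpoint recurrence, which agrees with every section that defines an analysis. An empty relapse curve for duration of CR is itself a sign that the literal reading was not meant.

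Most of this stands. It settles the intention as ever-CR and makes this a correction of wording. It does not remove the conflict. The group-by-group reading needs a *respectively* that the sentence lacks. Splitting only by analysis (nonresponder in the primary, recurrence in the secondary) still leaves relapsers as primary nonresponders. SAP 3.1 repeats the sentence, SAP 7.7 reports no changes from the protocol's analysis, and no section says which rule prevails.

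Three stronger readings are tempting, and the documents do not support them:

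- *The study is underpowered.* The losses in step 4 arise only if the overview sentence overrides the endpoint sections.
- *The futility look is compromised.* With a true CR rate of 40% and 20% of CRs already relapsed and dropped, P(10 or more of 35) would be 72.6% (rate 0.32) instead of 94.2%. The interim sections count patients who achieve a CR, so this too needs the overview sentence to override them.
- *The endpoint becomes CR held to Week 96.* Only observed disease is reclassified. A responder who leaves without relapse would still count.

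**Conclusion.** The contradiction is real, and the overview sentence is the side that is wrong. It is a misstated classification rule and not an error in the sample size. Under the ever-CR rule that the other sections support, the stated operating characteristics stand, apart from the small rounding difference at n = 70.

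If the sentence were followed, the CR rate would fall by the share of responders with observed relapse. From 28/70, the comparison with 20% changes once 7 or more responders (25%) are reclassified, and not before. All relapse shares used here are assumptions, and the probabilities further assume independent relapse and a single-stage test. This should be fixed before the interim look, while the choice cannot be influenced by observed relapses.

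**What to change.** In the Synopsis, Protocol 9.1 and SAP 3.1, change the analysis classification only and leave the discontinuation rule as it is. Suggested text:

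> Patients with baseline CIS and no documented CR in the primary endpoint window are non-responders in the primary analysis. A patient with a documented CR who later has CIS or high-grade disease remains a responder in the primary analysis and in the interim count, and is an event for duration of CR and EFS.

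In Protocol 7.5 and SAP 1, state that being a failure at later timepoints refers to EFS.

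The endpoint window must be reconciled separately, because the protocol closes it at Week 48 and SAP 5.1.1 and 7.3.1 set no upper limit. No extra row for response at Week 48 is needed, since SAP 7.3.1 already tabulates the proportion of baseline-CIS patients in response at that time.

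The cost is a replacement sentence in three places and a short clarification in two. No new data, visits or analyses are required.

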### 9.2 Discussion of Study Design and Choice of Control Group(s)

The presentations and discussion at a workshop held at the annual AUA meeting in May 2013 serve as the rationale for this study. A summary of that meeting was published by Jarow et al.

(2014). The FDA recently published a more detailed guidance document in February 2018 that reiterates the challenges for drug development in this specific population, clearly stating that there is currently no effective therapy for patients with high-grade NMIBC unresponsive to BCG other than cystectomy (FDA 2018). Therefore, a single-arm Phase 2 clinical study is acceptable.

### 9.3 Selection of Study Population

Eligible patients must be BCG-unresponsive, adequately treated, who after recurrence have had all papillary disease resected and CIS fulgurated when indicated.

#### 9.3.1 Inclusion Criteria

Eligible patients must meet the following inclusion criteria:

1. Male or female patients  $\geq 18$  years of age at the time of consent
2. Patient must have been adequately treated with BCG defined as at least one of the following (FDA 2018):
  - a. At least five of six doses of an initial induction course plus at least two of three doses of maintenance therapy
  - b. At least five of six doses of an initial induction course plus at least two of six doses of a second induction course
  - c. A single course of induction BCG can qualify if the patient has T1 high-grade disease at first evaluation (see 3c)
3. Patient must be BCG-unresponsive according to the FDA guidance defined as at least one of the following (FDA 2018):
  - a. Persistent or recurrent CIS alone or with recurrent Ta/T1 disease within 12 months of completion of adequate BCG therapy. An assessment within 15 months can also qualify when no assessment was done 12 months after completion of adequate BCG therapy.
  - b. Recurrent high-grade Ta/T1 disease within 6 months of completion of adequate BCG therapy. An assessment within 9 months can also qualify when no assessment was done 6 months after completion of adequate BCG therapy.
  - c. T1 high-grade disease at the first evaluation following a single course of induction BCG qualifies (Lerner et al. 2015, Steinberg et al. 2016)
4. Patient must have, at study entry, NMIBC indicated by 1 or more of the following:
  - a. Ta or T1 high-grade disease
    - i. No more than 42 days may elapse between the start of protocol therapy and complete resection of Ta/T1 papillary disease qualifying the patient for the study
  - b. CIS disease
    - i. Obvious areas of CIS should be fulgurated prior to start of therapy when indicated
5. Patient must have no known evidence of concomitant upper tract urothelial carcinoma or urothelial carcinoma within the prostatic urethra within 6 months of enrollment
6. Patient must have an Eastern Cooperative Oncology Group (ECOG) performance status  $\leq 2$

7. Patient must have adequate hematologic function, as demonstrated by the following:
  - a. Hemoglobin level  $\geq 10$  g/dL
  - b. Absolute neutrophil count  $\geq 1.5 \times 10^9$ /L
  - c. Platelet count  $\geq 100 \times 10^9$ /L
8. Patient must have adequate liver and renal function as demonstrated by the following:
  - a. Aspartate aminotransferase and alanine aminotransferase each  $\leq 3.0 \times$  upper limit of normal
  - b. Total bilirubin  $\leq 1.5 \times$  upper limit of normal, unless prior documentation of Gilbert's syndrome in which case, 3.0 mg/dL is allowed
  - c. Serum creatinine  $\leq 1.5 \times$  upper limit of normal or measured or calculated creatinine clearance  $\geq 30$  mL/min
9. Female patients of childbearing potential must use maximally effective birth control during the period of therapy (ie, a combination of 2 regulatory approved methods), must be willing to use contraception for 1 month after the last study drug infusion, and must have a negative urine or serum pregnancy test result upon entry into the study. Otherwise, female patients must be postmenopausal (no menstrual period for a minimum of 12 months) or surgically sterile
10. Male patients who are sexually active must be willing to use a double-barrier contraceptive method upon study enrollment, during the course of the study, and for 1 month after the last study drug infusion
11. Patient must be able to understand and sign an ICF
12. Patient must be able to comply with protocol requirements, including attendance at required clinic visits

